12.5.1 Efficacy and/or Pharmacodynamic endpoint(s)

Data for the secondary variables (*i.e.* total daily dose of insulin, insulin-dose adjusted HbA1c) will be descriptively summarized for each treatment group and each time point (where applicable).

Full remission will be defined by HbA1c $\leq 6.5\%$ (48 mmol/mol) and no exogenous insulin use, at 52 weeks (1 year). Two validated criteria will be used to assess partial remission including proportion of subjects with (1) Insulin Dose Adjusted HbA1c (IDAA1c) ≤ 9.0 (Mortensen et al 2009) and (2) HbA1c $< 7.0\%$ (53 mmol/mol) and total daily insulin dose < 0.5 units per kg per day (Couper and Donaghue 2009). Stimulated C-peptide AUC by MMTT at Week 72 will be analyzed in the same manner as the primary objective. The baseline*visit interaction term may also be considered for this model due to the follow-up.

The proportion of subjects with detectable C-peptide, rate of decline from baseline C-peptide, and time to undetectable C-peptide will be descriptively summarized with estimates and confidence intervals for each treatment group and each time point (where applicable).

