12.8 Sample size calculation

12.8.1 Primary endpoint(s)

The sample size calculation is based on the primary endpoint of stimulated C-peptide AUC by the standard MMTT.

In [Greenbaum \(2012\)](#) the average baseline stimulated C-peptide AUC by MMTT is approximately 0.7 pmol*hr/mL. They show a linear decline in untreated subjects resulting in an average AUC of 0.4 pmol*hr/mL at one year. It is assumed that a clinically significant prevention of decline would occur if the rate of decline was one half (50%) of that of untreated subjects. Thus, a clinically relative improvement due to treatment would occur if the AUC at 1-year was 37.5% larger for treatment than placebo ($0.55/0.4 = 1.375$). Starting with 44 subjects and accounting for ~18% dropout rate, a total of 36 subjects randomized in a 2:1 ratio (stratified by age at first screening visit: ≥ 18 to 21 years, ≥ 12 to < 18 years) between CFZ533 and placebo provides 55% power to detect an improvement over placebo using a one-sided alpha=0.1 test when the true ratio of treatment to placebo is 1.375 (Note: if the rate of decline in treatment vs placebo is instead 75% less, corresponding to a ratio of 1.56, the power is 75%). This calculation assumes a coefficient of variation of 70% for the AUC; the standard deviation of log (AUC) was derived from the relationship between the CV and variance parameter for the lognormal distribution. This assumption was the result of the observed CV% of 5 TrialNet studies in T1DM subjects ([Bundy et al 2016](#)).

13 Ethical considerations and administrative procedures

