6.2.1 Variables

- Normalized stimulated C-peptide AUC_{0-2 hrs} by MMTT at Week 72.
- Average of Total daily dose of insulin

Total daily dose of insulin for a given day is the total daily units of insulin (adding insulin pump total basal units per day, insulin pump total bolus units per day and total units insulin injection (syringe) units per day) adjusted per body weight (unit/Kg/24 h). This information will be recorded at the site for at least 3 days and up to 7 days prior to each visit, as available (See Site Operations Manual). The average of total daily units of insulin per day (at each visit) will be calculated.

- Insulin-dose adjusted HbA1c (IDAA1c) ([Andersen et al 2014](#)).

IDAA1C = HbA1C (percent) + 4 × [insulin dose (units per kg per day)].

If HbA1c is stated in mmol/mol, it can be converted to percent by the following formula:
HbA1c % = (HbA1c mmol/mol × 0.0915) + 2.15.

- Remission at 52 weeks defined by meeting any of the below criteria:
 - Full remission defined by HbA1c ≤ 6.5% (48 mmol/mol) and no exogenous insulin use at 52 weeks.
 - Partial remission defined by Insulin Dose Adjusted HbA1c (IDAA1c) ≤ 9.0 ([Mortensen et al 2009](#))
 - Partial remission defined by HbA1c < 7.0% (53 mmol/mol) and total daily insulin dose < 0.5 units per kg per day ([Couper and Donaghue 2009](#)).
- The proportion of subjects with detectable C-peptide and time to undetectable C peptide. Undetectable C-peptide is defined as all timed values on the MMTT below the LLOQ.
- The proportion of subjects with Peak C-peptide ≥ 0.2 pmol/mL and time to Peak C-peptide < 0.2 pmol/mL (or below LLOQ)
- Rate of decline from baseline C-peptide

A linear mixed model regression of the log transformed stimulated C-peptide AUC, including baseline assessment, on time expressed in years (time = 1 at Week 52 and 0 at baseline) will be performed. The mixed model will include treatment effect, time by treatment interaction with time as continuous variable and subject as random effect. The estimates of the yearly rate of decline by treatment and their 80% confidence intervals will be obtained after back transformation (exponential) of the estimates of the slopes.

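### Applied literally, SAP 6.2.1 labels the proportion of C-peptide AUC retained per year as the yearly rate of decline, so the arm that declines more slowly gets the larger figure

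*SAP*

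**What the plan says.** Protocol 12.5.1 promises that the "rate of decline from baseline C-peptide, and time to undetectable C-peptide will be descriptively summarized with estimates and confidence intervals" for each arm, but gives no formula. Protocol 8.2.1 also names the quantity without defining it. The only definition in the supplied text is in SAP 6.2.1.

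- Model: "A linear mixed model regression of the log transformed stimulated C-peptide AUC, including baseline assessment, on time expressed in years".
- Time scale: "time = 1 at Week 52 and 0 at baseline".
- Terms: "The mixed model will include treatment effect, time by treatment interaction with time as continuous variable and subject as random effect". Each arm therefore has its own slope.
- Reported quantity: "yearly rate of decline by treatment and their 80% confidence intervals will be obtained after back transformation (exponential) of the estimates of the slopes".

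The section does not go on to subtract from one, state a percentage scale or rename the result.

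Protocol 12.8.1 shows what the plan means by decline. It assumes that "a clinically significant prevention of decline would occur if the rate of decline was one half (50%) of that of untreated subjects". There the rate of decline is an amount lost, and a smaller value is better.

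**The concern.** In a regression of log AUC on years, the exponentiated slope is a year-on-year ratio. A value near 1 means that almost nothing was lost, and a value near 0 that almost everything was. Reported as a rate of decline, it runs opposite to its name and to the protocol's use of the term.

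SAP 6.1.3 applies the same exponential back-transformation in the primary analysis and correctly calls the results geometric means and a ratio. Only in 6.2.1 does the label fail to match the quantity.

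Two features make the slip easy to miss. First, Protocol 1.1 says that pediatric patients lose about 50% of residual function in the first year, so a placebo figure of 0.571 labelled as decline would look plausible. Second, the confidence limits must change places when retention is converted to loss, and a programmer working from this sentence alone would not do that.

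At stake is whether a supporting efficacy figure can be read in the right direction.

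**Working it through.** **Inputs (Protocol 12.8.1).** For the baseline, "the average baseline stimulated C-peptide AUC by MMTT is approximately 0.7 pmol*hr/mL". For untreated subjects, "They show a linear decline in untreated subjects resulting in an average AUC of 0.4 pmol*hr/mL at one year". The coefficient of variation is 70%, with 36 evaluable subjects in a 2:1 ratio (24 and 12) and one-sided alpha 0.1.

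**Step 1: reproduce the plan's figures.**
- Half the decline: 0.7 - 0.5 x (0.7 - 0.4) = 0.55, and 0.55/0.4 = 1.375, as stated.
- 75% less decline: 0.7 - 0.25 x 0.3 = 0.625, and 0.625/0.4 = 1.5625, stated as 1.56.
- SD of log AUC = sqrt(ln(1 + 0.7^2)) = 0.6315.
- With non-centrality ln(ratio) / (0.6315 x sqrt(1/24 + 1/12)) and 34 degrees of freedom, the noncentral t gives power of 55.1% at 1.375 and 75.4% at 1.56. The protocol states 55% and 75%.

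The planning values are therefore coherent and can be used for the check.

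**Step 2: apply SAP 6.2.1 to them.** Slope = ln(AUC at 1 year / 0.7).

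| Scenario | AUC at 1 year | Slope | exp(slope), as written | 1 - exp(slope), yearly loss |
|---|---|---|---|---|
| Placebo | 0.40 | -0.560 | 0.571 | 42.9% |
| CFZ533, half the decline | 0.55 | -0.241 | 0.786 | 21.4% |
| CFZ533, 75% less decline | 0.625 | -0.113 | 0.893 | 10.7% |

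The better the assumed effect, the larger the number the written rule labels as decline.

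**Step 3: does this depend on the values or the visits?** No. The exponential is an increasing function, so the arm with the flatter slope always has the larger exp(slope). Fitting the log-linear slope to the protocol's straight-line decline at Weeks 0, 12, 24, 36 and 52 gives 0.572 and 0.786. SAP 6.2.1 does not list the visits for this model. If Week 72 is added, and the straight line is assumed to continue to that visit, the values are 0.525 and 0.776. The direction is the same.

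**Step 4: confidence limits.** If the slope has 80% limits L to U, the loss has limits 1 - exp(U) to 1 - exp(L). As an illustration, assume a standard error of 0.1 for the placebo slope (not a figure from the documents). Then exp(slope) has limits 0.503 to 0.650, and the loss has limits 35.0% to 49.7%. The exchange of limits holds for any standard error.

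**The case against.** The best defence is that the SAP says the estimates are obtained *after* exponentiation, which leaves room for a last step that was not written down. SAP 1.1 places table shells and derived-variable specifications in separate documents that were not supplied. A statistician may well intend 1 - exp(slope). This stands to the extent that the final output cannot be predicted. It does not rescue the sentence, because the exponential is the only transformation stated and the direction of the result should not depend on an unwritten step.

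It is also fair to say that little rests on this figure. Rate of decline is not among the endpoints in Protocol Table 2-1 or SAP 1.3.2, Protocol 12.5.1 treats it descriptively, and no test or decision rule in the supplied text uses it. The planned change from baseline, ratio to baseline and model-based CFZ533-to-placebo ratio (SAP 6.1.2 and 6.1.3) all run the right way and would expose a reversed figure. That stands, and it limits the importance of the point.

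A reader might infer three stronger things that the documents do not support:

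- **That the study report will show the drug as worse.** The table shells are not available, so this cannot be said. The claim is only about what the written rule yields.
- **That this model estimates the effect on which the trial is powered.** Protocol 12.8.1 turns the halved decline into a one-year ratio of 1.375, and the primary repeated-measures model estimates that ratio. The protocol's decline is also linear in AUC, while SAP 6.2.1 models a proportional one. The two agree on a halving here because both arms start at 0.7 and the horizon is one year.
- **That a misleading between-arm ratio of rates will be reported.** SAP 6.2.1 specifies estimates by treatment only.

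**Conclusion.** Wrong as written, with limited reach. Taken literally, SAP 6.2.1 reports retention as decline, and the direction is reversed for any data. On the protocol's planning values the size is 0.571 and 0.786 under the decline label, against true yearly losses of 42.9% (placebo) and 21.4% (CFZ533).

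The reversal rests only on the SAP's model (log AUC on years) and on the protocol's use of decline to mean loss. The numerical size also rests on the planning values of 0.7, 0.4 and 0.55. The model fit is sound, and only the stated conversion and its name are at fault. The primary analysis, the power and the sample size do not change.

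**What to change.** In SAP 6.2.1, do one of the following:

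1. Define the yearly rate of decline as 100 x (1 - exp(slope))%, with 80% limits from 100 x (1 - exp(upper slope limit)) to 100 x (1 - exp(lower slope limit)).
2. Keep exp(slope) with its limits in their natural order, and label it the proportion of AUC retained per year.

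The first option matches the term used in the protocol. Under either option, make the table shell and the derived-variable specification agree with the SAP. The cost is one sentence in the SAP and a check of the shell, with no new data or modelling and no change to the protocol.

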6.2.2 Descriptive analyses

- For stimulated C-peptide AUC by MMTT at Week 72, total daily dose of insulin, insulin-dose adjusted HbA1c, their change and percent from baseline will be summarized by descriptive statistics for each treatment group and each time point (where applicable).

- The proportion of subjects with remission and each of the three components (full remission and two different criteria for partial remission) and subjects with detectable C-peptide will be descriptively summarized for each treatment group and each time point and overall study period.
- Time to undetectable C peptide will be analyzed by Kaplan-Meier methods by treatment group. Estimates of median time to undetectable C peptide and proportion of subjects with detectable C-peptide and their confidence intervals for each treatment group and each time point (where applicable) will be produced. Time to Peak C-peptide \leq 0.2 pmol/mL (or below LLOQ) and proportion of subjects with C-peptide \geq 0.2 pmol/mL will be analyzed similarly.

6.2.2.1 Graphical presentation of results

Model-based geometric mean (80% CI) of stimulated C-peptide AUC by MMTT will be plotted by treatment and time point.

Arithmetic mean (80% CI) of insulin-dose adjusted HbA1c and total daily dose of insulin will be plotted by treatment and time point.

Graphical presentation of Kaplan-Meier estimate of proportion of subjects with detectable C-peptide will be plotted by treatment.

6.2.3 Statistical model, assumptions and hypotheses

Normalized stimulated C-peptide AUC by MMTT at Week 72 will be analyzed in the same manner (and using the same model) as the primary objective. C-peptide AUC at all time points up to and including Week 72 will be included. The baseline by visit interaction term may also be considered for this model.

6.2.3.1 Model checking procedures

Model checking procedures for stimulated C-peptide AUC by MMTT at Week 72 will be the same as for primary analysis, refer to [Section 6.1.3.1](#).

6.2.3.2 Graphical presentation of results

Model estimated treatment geometric means for stimulated C-peptide AUC by MMTT at Week 72 and ratio between treatment and their 80% CI will be plotted over time, by visit.

Commercially Confidential Information

Commercially Confidential Information

Commercially Confidential Information

Commercially Confidential Information

Commercially Confidential Information

7 Statistical methods for safety and tolerability data

All subjects within the Safety set will be included in the safety data analysis. Safety outputs will be produced by treatment.

7.1 Variables

Safety variables include adverse events, vital signs (blood pressure [SBP and DBP] and pulse), height and weight, ECG intervals, laboratory measurements (hematology, clinical chemistry, urinalysis, coagulation panel, virology and viral serology for SARS-CoV-2, CMV, EBV, and HSV), as well as subject demographics, baseline characteristics, and treatment information.

Safety summaries (tables, figures) include only data from the on-treatment period with the exception of baseline data which will also be summarized where appropriate (e.g. change from baseline summaries). In particular, summary tables for adverse events (AEs) will summarize only on-treatment events, with a start date during the on-treatment period (*treatment-emergent* AEs).

For all safety data listings (e.g. ECG, lab, vital signs, AEs), data collected during the post-treatment period will be flagged.

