Study design	
CCFZ533X2207 is a Phase 2, non-confirmatory, investigator- and subject-blinded, randomized, placebo-controlled study to evaluate the safety, tolerability, pharmacokinetics, and efficacy of CFZ533 on preservation of residual pancreatic β-cell function in new onset T1DM in pediatric and young adult subjects.
 
The study is planned for 44 subjects randomized and assuming $\sim 18\%$ dropout rate, 36 subjects for primary efficacy (at 52 weeks) and safety endpoints (at 72 weeks).
 
Eligible subjects will be enrolled and randomized to active or placebo in a 2:1 ratio, stratified by age at first screening visit (≥ 18 to 21 years, followed by ≥ 12 to < 18 years).
 
The study timeline includes a screening period of approximately 8 weeks, a baseline period of 2 weeks, a treatment period of 52 weeks and a follow-up period following last dose of CFZ533 of 20 weeks.
 
This study will be the first study to evaluate CFZ533 in a pediatric population in any indication. Thus, enrollment will be staggered to evaluate safety and

	
tolerability on a rolling basis and enable gradual enrollment of younger age and lower weight groups.
 
The PK profile of CFZ533 will be evaluated throughout the study (Month 3, 6 and 9). Dosage adjustments may be introduced based on emerging PK data. The current assumptions considered allometric scaling based on body weight. The PK assumptions will be confirmed using population PK modelling.
 
Sequential enrollment by age and body weight (BW) categories include:
 
 • Cohort 1: age ≥ 15 to ≤ 21 years (older adolescents to young adults), body weight ≥ 40 kg to ≤ 125 kg. • Cohort 2: age ≥ 12 to ≤ 21 years (adolescents to young adults), body weight ≥ 30 kg to ≤ 125 kg. 
Before opening a subsequent cohort, safety and tolerability data from at least 6 subjects in Cohort 1 must be reviewed and deemed safe to proceed by the Sponsor and Lead Investigator.

Population	
The study population will be comprised of newly diagnosed T1DM pediatric and young adult subjects.
 
Forty-four subjects between the ages of 12 and 21 (inclusive) will be enrolled and randomized in the study in sequential order as outlined in the study design.

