	
expected pharmacology effect has returned to baseline, whichever is longer; or longer if required by local regulations.
 
 Chronic infection with Hepatitis B (HBV) or Hepatitis C (HCV). A positive HBV surface antigen (HBsAg) test, or if standard local practice, a positive HBV core antigen test, excludes a subject. Subjects with a positive HCV antibody test should have HCV RNA levels measured. Subjects with positive (detectable) HCV RNA should be excluded Evidence of Epstein-Barr Virus (EBV), Cytomegalovirus (CMV), Herpes simplex virus (HSV), or coronavirus SARS-CoV-2 by viral load above laboratory threshold or only positive IgM serology in the absence of positive IgG, suggestive of active or recent infection. Any of the following abnormal laboratory values at screening: 
 total white blood cell count (WBC) outside the range of 1,500-15,000/mm³ (1.5-15.0 x 10⁹/L). neutrophil count (<1500/mm³) (<1.5 X 10⁹ / L). lymphocyte count <500/mm³ (<0.5 X 10⁹ / L). hemoglobin (Hgb) <8.0 g/dL. platelets <100,000/mm³ (<100 x 10⁹/L).
Study treatment	
Subjects will be assigned to one of the 2 treatment arms in a ratio of 2:1, CFZ533 or matching placebo, stratified by age at first screening visit (≥ 18 to 21 years and ≥ 12 to < 18 years).
 
For the single intravenous (IV) loading dose, all subjects receive the same dose: CFZ533 30 mg/kg IV on Study Day 1.
 
For the subcutaneous (SC) maintenance regimen, a fixed CFZ533 dose by body weight (BW) category will be administered every week from Day 8 (Week 1) up to Week 51 (last dose). Last dose is administered at CCI and the end of the treatment assessment will be performed at Week 52.
 
 BW category II (≥ 30 to < 50 kg): 195 mg (1 injection of 1.3 mL) SC weekly. BW category III (≥ 50 kg): 300 mg (1 injection of 2 mL, or 2 injections of 1 mL) SC weekly. 
*note earlier versions of the protocol included body weight in the 20 to 30 kg range, which would have been in a Body weight Category I. This lower body weight category is no longer included and explains the nomenclature of weight categories II and III only.

Efficacy assessments	
 C-peptide during MMTT.
Pharmacodynamic assessments	
 Soluble CD40 (sCD40) concentrations in plasma (target biology and target engagement in whole blood) at baseline, during treatment and follow-up period.

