Commercially Confidential Information

Glycemic measures and insulin dosage may be obtained from device records (*i.e.* meter and Commercially Confidential Information glucose and insulin pump downloads for insulin dosing) if available. Date and time of study drug dosing will also be captured in a study diary.

[figure not shown]
Safety assessments will include height, weight, vital signs, physical examination, ECGs, standard clinical laboratory evaluations of hematology, blood chemistry, urinalysis, viral load and serology, adverse events and serious adverse events. Additional safety assessments for children and adolescents include: Tanner stage, growth velocity, and serial bone ages. Blood samples will also be taken for inflammatory CCI biomarkers at various time points during the study, as indicated in the Assessment Schedule, [Table 8-1](#).

Subjects must be instructed to use their own insulin as this is part of standard of care and not part of the study. Insulin management including dose adjustments will be made by the subject's care provider according to local guidelines and individualized glycemic targets.

Minimum safety monitoring for each subject will be performed at least CCI post-last dose of CFZ533 or placebo, a time when pharmacodynamic response is anticipated to have returned to the subject's baseline. However, subjects will be followed until week 72, 20 weeks post dose, to assess safety and effects on pancreatic β -cell function after stopping the investigational drug.

Reviews of safety and pharmacokinetic (PK) data will be jointly completed by the Sponsor (limited unblinding) and Lead Investigator (blinded) (see [Section 6.5](#) and [Section 12.7](#)). The safety evaluation will include all SAEs and AEs, laboratory evaluations, and ECGs. Cohort expansion will be based on the following:

- To open Cohort 2: At least CCI (aged 15 to \leq 21 years) of Cohort 1 treated with CFZ533 or placebo CCI along with the safety data for all subjects enrolled up to that point, must be reviewed and deemed satisfactory jointly by the sponsor and Lead Investigator. Assessment of CCI subjects in this cohort, as opposed to CCI in other cohorts, is because existing safety data is more robust for subjects in this age and weight range population.

Figure 3-1 Study Design

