12.4.1 Definition of primary endpoint(s)

All safety data, including laboratory measurements, vital signs, adverse events, and ECGs are considered primary endpoints for the first primary objective.

Stimulated C-peptide AUC by mixed meal tolerance test (MMTT) after 52 weeks, normalized by the duration of measurements, is the primary endpoint for the second primary objective. This endpoint is derived from the blood samples taken for C-peptide determination over the course of 2 hours. The AUC will be logarithmically transformed prior to analysis.

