12.4.2 Statistical model, hypothesis, and method of analysis

Safety

- Vital signs

All vital signs data will be listed by treatment, subject, and visit/time and if ranges are available abnormalities (and relevant orthostatic changes) will be flagged. Summary statistics will be provided by treatment and visit/time.

- ECG evaluations

All ECG data will be listed by treatment, subject and visit/time, abnormalities will be flagged. Summary statistics will be provided by treatment and visit/time.

- Clinical laboratory evaluations

All laboratory data will be listed by treatment, subject, and visit/time and if normal ranges are available abnormalities will be flagged. A separate listing is provided presenting all parameters in a subject with any abnormal values. Summary statistics will be provided by treatment and visit/time.

- Adverse events

All information obtained on adverse events will be displayed by treatment and subject.

The number and percentage of subjects with adverse events will be tabulated by body system and preferred term with a breakdown by treatment. A subject with multiple adverse events within a body system is only counted once towards the total of this body system and treatment.

The number and percentage of subjects with adverse events by maximum severity of adverse events will be tabulated by body system and preferred term with a breakdown by treatment.

The number and percentage of subjects with adverse events classified as related to study drug will be tabulated by body system and preferred term with a breakdown by treatment.

Stimulated C-peptide AUC

Stimulated C-peptide AUC by the standard MMTT, normalized by the duration of measurements, will be analyzed with a mixed model repeated measures analysis and the primary objective will be examined with the results of this analysis at the 52 week time point. The natural log of the AUC will be the dependent variable in this analysis. Independent variables will include age, treatment, visit, and the treatment by visit interaction. The natural log of the baseline AUC will be used as a covariate and subject will be used as a random effect. Least square geometric mean and geometric mean ratio to baseline of each treatment, the ratio of CFZ533 to placebo, the 80% confidence interval of the ratio, and the one-sided p-value of treatment benefit will be presented for each time point.

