4.1.1 General definitions

On-treatment assessment/event

The overall observation period will be divided into three mutually exclusive segments:

1. ***pre-treatment period***: from day of subject's informed consent to before date of first administration of study treatment
2. ***on-treatment period***: from date of first administration of study treatment to 98 days after date of last administration of study treatment (including start and stop date)
3. ***post-treatment period***: starting at day 98+1 after last administration of study treatment.

Note: If dates are incomplete in a way that clear assignment to pre-, on-, post-treatment period cannot be made, then the respective data will be assigned to the on-treatment period.

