All ECG data will be listed by treatment, subject and visit/time, abnormalities will be flagged. Summary statistics will be provided by treatment and visit/time.

Clinical laboratory evaluations

Listing of all laboratory parameters will be provided in subjects with abnormal values. Summary statistics will be provided by treatment and visit/time. Shift table will be provided.

Adverse events

All information obtained on adverse events will be displayed by treatment and subject.

The number and percentage of subjects with adverse events will be tabulated by body system and preferred term with a breakdown by treatment. A subject with multiple adverse events within a body system is only counted once towards the total of this body system and treatment. Similar information will also be presented by preferred term.

The number and percentage of subjects with adverse events by maximum severity of adverse events will be tabulated by body system and preferred term with a breakdown by treatment.

The number and percentage of subjects with adverse events classified as related to study drug will be tabulated by body system and preferred term with a breakdown by treatment. Similar analysis will be performed for serious adverse events, and adverse events leading to treatment discontinuation.

ClinicalTrials.gov and EudraCT

For the legal requirements of ClinicalTrials.gov and EudraCT, two required tables on treatment emergent adverse events which are not serious adverse events with an incidence greater than 5% and on treatment emergent serious adverse events and SAE suspected to be related to study treatment will be provided by system organ class and preferred term on the safety set population and prepared internally by Novartis.

If for a same subject, several consecutive AEs (irrespective of study treatment causality, seriousness and severity) occurred with the same SOC and PT:

- a single occurrence will be counted if there is ≤ 1 day gap between the end date of the preceding AE and the start date of the consecutive AE
- more than one occurrence will be counted if there is > 1 day gap between the end date of the preceding AE and the start date of the consecutive AE

For occurrence, the presence of at least one SAE / SAE suspected to be related to study treatment / non-SAE has to be checked in a block e.g., among AE's in a ≤ 1 day gap block, if at least one SAE is occurring, then one occurrence is calculated for that SAE.

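### Safety tables and figures stop 98 days after the last dose (Week 65 in completers), so the last 7 weeks of safety follow-up have no visible summary by arm

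*SAP*

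**What the plan says.** SAP 4.1.1 defines the on-treatment period as running "from date of first administration of study treatment to 98 days after date of last administration of study treatment", both ends included. Everything later is post-treatment. SAP 7.1 then applies that period to the safety outputs: "Safety summaries (tables, figures) include only data from the on-treatment period with the exception of baseline data". The adverse event tables count only events that start inside it. In listings, post-treatment data are flagged.

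The protocol describes a longer horizon.

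- Synopsis, Study design: the planned numbers are "36 subjects for primary efficacy (at 52 weeks) and safety endpoints (at 72 weeks").
- Section 3: "subjects will be followed until week 72, 20 weeks post dose, to assess safety", among other purposes. Sections 9.2 and 10.1.1 continue safety monitoring and adverse event collection to the end of the study.
- Section 12.4.1: "All safety data, including laboratory measurements, vital signs, adverse events, and ECGs are considered primary endpoints for the first primary objective".
- Section 12.4.2: summary statistics for laboratory data, ECGs and vital signs by treatment and visit, and adverse event tables by treatment, with no limit on period.
- Section 10.1.3: events after a redacted post-dose interval are still collected. They will generally not be attributed to the drug, but they may help to show benefit from preserved beta-cell function.

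One visible item in the SAP reaches further. Section 7.2 says that change in height, weight and BMI z-scores by treatment at Week 72 may be provided if the data allow.

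**The concern.** Safety is a primary objective, and this is the first paediatric study of the drug. The protocol keeps subjects under observation to Week 72 partly for safety, yet the SAP rule takes the final stretch of that observation out of every safety table and figure.

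Listings show what happened to each subject. They do not put the two arms side by side with denominators. Any question about late events that depends on the contrast between arms, including the possible benefit named in Section 10.1.3, would have to be answered by counting through listings. The SAP presents itself as implementing the protocol's analysis, and its visible text does not explain the narrower scope.

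**Working it through.** **Inputs**

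- Cut-off: last dose + 98 days (SAP 4.1.1).
- Last dose in completers: the synopsis gives weekly dosing "every week from Day 8 (Week 1) up to Week 51 (last dose").
- Dosing range: 3 days either side, and up to 6 days late before a dose counts as missed (Protocol 6.1).
- Follow-up visits: Weeks 56, 60, 64, 68 and 72. Week 68 is Day 477 ±7 (Protocol Table 8-1).

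**Reproducing the visit days.** Study day = 7 × week + 1. This gives Day 365 for Week 52, 393 for Week 56, 421 for Week 60, 449 for Week 64 and 477 for Week 68, all as printed. By the same rule Week 51 is Day 358 and Week 72 is Day 505.

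**Cut-off in completers**

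- Nominal: 358 + 98 = Day 456, and (456 − 1)/7 = Week 65.
- Last dose 3 days early: 355 + 98 = Day 453.
- Last dose 6 days late: 364 + 98 = Day 462.
- Earliest Week 68 visit: 477 − 7 = Day 470, which is 470 − 462 = 8 days after the latest of these cut-offs.

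For the earliest Week 68 visit to fall inside the window, the last dose would have to be on Day 470 − 98 = Day 372 (Week 53) or later. So the result does not depend on the exact Week 51 date. A last dose at Week 52 would give 365 + 98 = Day 463, still before Day 470.

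**What lies outside in a completer (nominal)**

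- Days: 505 − 456 = 49, out of 505 − 358 = 147 after the last dose. 49/147 = 33%.
- Weeks: 72 − 65 = 7, out of 72. 7/72 = 9.7%.
- Visits: 2 of the 5 follow-up visits.
- Subject-time, if all 36 planned subjects complete and split 2:1 into 24 and 12: 24 × 7 + 12 × 7 = 168 + 84 = 252 subject-weeks. 252 × 7/365.25 = 4.8 subject-years.

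**Subjects who stop drug early but stay in follow-up**

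| Last dose | Cut-off day | Cut-off week |
|---|---|---|
| Week 12 (Day 85) | 85 + 98 = 183 | 26 |
| Week 24 (Day 169) | 169 + 98 = 267 | 38 |
| Week 36 (Day 253) | 253 + 98 = 351 | 50 |

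The documents do not say how many such subjects to expect, so no total is given for them.

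**The case against.** The case for leaving the SAP as it stands has real weight.

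- **The rule is a normal one.** A treatment-emergent window is standard practice. Ninety-eight days is 14 weeks, the same interval as the contraception requirement in exclusion criterion 22. Section 10.1.3 says that late events will generally not be put down to the drug. This stands, and nothing here argues for another window in the main tables.
- **The primary safety analysis is tied to the end of treatment.** Section 12 bases it on subjects who reached Week 52 or stopped early. This also stands, but that sentence sets no limit on which safety data are later summarised, and the SAP's own window already runs past Week 52. The synopsis places the safety endpoints at 72 weeks.
- **The data are still listed.** Adverse events, ECGs and vital signs appear in listings by treatment and subject, with late records flagged. With 44 subjects these can be read directly. So a reader who infers that late safety data are lost would be going further than the documents allow. What is missing is the summary by arm.
- **Parts of the plan cannot be seen.** Text is redacted before SAP Section 7 and at the end of 7.2, and the table shells are a separate document. Severe hypoglycaemia and ketoacidosis are named as outcome measures in Protocol 4.3.1 and may be compared by arm there. The finding is therefore limited to the visible text.

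A reader might also infer that normal late laboratory results reach no output at all. Protocol 12.4.2 says "All laboratory data will be listed by treatment, subject, and visit/time" and adds a separate listing for subjects with abnormal values. SAP 7.2 keeps only the latter: "Listing of all laboratory parameters will be provided in subjects with abnormal values". The natural reading of that sentence is per subject. Every subject has type 1 diabetes, and glucose is in both the chemistry panel and the urinalysis (Sections 8.3.2.1 and 8.3.2.3). Nearly every subject should therefore have an abnormal value and be listed in full. The wording differs from the protocol and should be aligned, but the practical loss is likely to be small.

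**Conclusion.** The point holds in a limited form. In completers, adverse events starting in about the last 7 weeks and everything collected at Weeks 68 and 72 fall outside the safety tables and figures that the SAP describes. The only visible exception is the optional growth summary. That is one third of the time after the last dose, and more in subjects who stop drug early but remain in follow-up. This falls short of the protocol's 72-week safety horizon, and the possible benefit named in Section 10.1.3 calls for a comparison between arms that flagged listings do not give.

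The conclusion rests on a last dose at or near Week 51 and on the visible text only. The documents do not support saying that the 98-day rule is wrong, that late safety data are lost, or that a drug effect would be missed. No event rate is given, so the number of events left out of the tables cannot be stated. The change should be made because it is cheap and safety is a primary objective. It does not touch the efficacy analysis or the main safety tables.

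**What to change.** Keep the 98-day treatment-emergent tables as the main set. Amend SAP 7.1 to add a set labelled supplementary, by arm, from first dose to the end-of-study visit, or for the post-treatment period on its own. It should cover adverse events, serious adverse events, laboratory data, ECGs and vital signs as collected, with the number of subjects observed at each visit.

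Two smaller edits belong with it:

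- In SAP 7.2, restore the full laboratory listing of Protocol 12.4.2, or say that it is dropped and why.
- In SAP 7.1, state that the optional Week 72 growth z-score summary in 7.2 is an exception to the on-treatment rule.

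The cost is one repeated set of tables from existing programs, one listing and a wording change, best made before database lock. The downside is that events after washout are harder to attribute to the drug, which is why the added set should carry the supplementary label. If the redacted text or the table shells already contain such summaries, a cross-reference in 7.1 is enough.
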